2.13.2 Twelve-Week Post Final Treatment Visit; 12 Weeks \pm 2 weeks

The following activities will be performed at the 12-Week visit:

- a) Obtain weight.
- b) Assess for adverse events.
- [REDACTED]
- [REDACTED]
- d) Optional - Obtain standard 2D imaging of treatment areas
- e) Subject Completes SGAIS questionnaire
- f) Subject completes Body Satisfaction Scale for abdomen and/or Body Satisfaction Scale for buttocks as appropriate.
- [REDACTED]

2.13.3 Optional Follow-Up Evaluations (up to 4 within study period)

The full evaluation is not required at optional follow-up visits; the extent of the assessment will be at the discretion of the Investigator.

Table 2 summarizes the study schedule and events at each visit.

Table 2. Schedule of Visits

	Screening (< 1hr)	Photo Visit (<1hr)	EMS Treatment #1 (<4hrs)	EMS Treatment #2 (<4hrs)	EMS Treatment #3 (<4hrs)	EMS Treatment #4 (<4hrs)	4-Wk Follow-Up (< 1 hr)	12-Wk Follow-Up (< 1 hr)	Optional Follow-Up**
Time Frame	Day -60 to 0	Day -30 to 1	Week 1 (Day0)	Week 1	Week 2	Week 2	Week 4 (\pm 1 weeks)	Week 12 (\pm 2 weeks)	Open
Informed Consent*	X								
Eligibility Criteria	X		X	X	X	X			
Medical History	X								
Height & BMI	X								
Weight	X	X	X				X	X	
3D Photos and/or tape measurements		X				X#	X	X#	
2D Photos		X				X#	X	X#	
EMS			X	X	X	X			
[REDACTED]			X	X	X	X	X	X	
AE Assessment			X	X	X	X	X	X	
BSQ*** per body area			X			X	X	X	
[REDACTED]							X	X	
Subject GAIS							X	X	

* Informed Consent to be signed by subject prior to the collection of any data or initiation of any study procedures.

** Investigator discretion as to timing and extent of follow-up assessment for optional visits.

*** BSQ (Body Satisfaction Questionnaire)

Optional

2.14 Assessments

Study-related assessments are described below.

2.14.1 Global Aesthetic Improvement Scale (GAIS-Subject)

At 4-Weeks post-final treatment, subjects will be asked to rate the improvement observed in the treated area(s) using the Global Aesthetic Improvement Scale:

- 3 = Very much improved
- 2 = Much improved
- 1 = Improved
- 0 = No change
- -1 = Worse
- -2 = Much worse
- -3 = Very much worse

2.14.2 Body Satisfaction Questionnaire – Abdomen

At 4-Weeks post-final treatment, the subjects' feeling about the shape and appearance of their abdomen will be assessed using the Body Satisfaction Questionnaire. The scale measures body image using a set of ten dichotomous items used to describe aspects of shape and appearance. The items are rated on a five-point semantic differential scale.

2.14.3 Body Satisfaction Questionnaire – Buttocks

At 4-Weeks post-final treatment, the subjects' feeling about the appearance of their buttocks will be assessed using the Body Satisfaction Questionnaire. The scale measures body image using a set of ten dichotomous items used to describe aspects of shape and appearance. The items are rated on a five-point semantic differential scale.

2.14.4 Photography

Three-Dimensional (3-D) photography will be used in this evaluation and may be performed using a commercially available photography system, such as the Quantificare LifeViz Body or similar device.

In addition, standardized photos of the treatment areas will be obtained at pre-treatment and 4-week visits, using standardized setup, lighting, and camera settings

to ensure consistency. All standard photographs will be captured at fixed angles and posture. Using a series of pre-determined markings on the floor, the photographer will position the camera at the pre-determined reference points to ensure that the reproduction ratio and focal distance are maintained throughout the image series during the study. A subject Foot Positioning Guide (FPG) will be used to standardize images of each body angle. During follow-up visits, the photographer will re-align subjects on the FPG by referencing baseline images.

[REDACTED]

[REDACTED]

[REDACTED]

[REDACTED]

[REDACTED]

[REDACTED]

[REDACTED]

[REDACTED]

[REDACTED]

2.14.7 Photograph Review

Independent physician(s) experienced in body contouring treatment may review study photographs to evaluate the outcome of treatment.

2.15 Endpoints

[REDACTED]

[REDACTED]

2.15.1 Primary Endpoints

The primary endpoints of the study will be defined as follows:

- Efficacy endpoint: Measurement of subject feeling about body shape, assessed using the Body Satisfaction Questionnaire at the 4-Week follow-up visit.
- Safety endpoint: The frequency of device-related adverse events (AEs) including device-related serious adverse events (SAEs) will be summarized.

2.15.2 Secondary Endpoints

- Subject-graded improvement in the treated area using the Subject Global Aesthetic Scale (SGAIS) at the 4-Week follow-up visit.

2.16 Statistical Analysis Plan

2.16.1 Statistical Methods: Overall Plan

Data will be summarized based on the nature of the data. Dichotomous (e.g., gender, independent photographic review) and ordinal (e.g., Fitzpatrick Skin type) data will be tabulated by category. The mean, standard deviation, maximum and minimum will be tabulated for continuous data (e.g., age). The significance level will be two-sided 0.05 for all statistical tests.

2.16.2 Analysis Population

Analysis Populations are defined as following:

Per-protocol Population (PP):

The Per-protocol Population will consist of all treated subjects followed for 4 Weeks and with weight change of no more than five percent (5%) of total body weight at the time the 4-Week images are taken compared to the weight taken at the first treatment visit. Since significant weight change may affect the effectiveness of the treatment, the primary efficacy analysis will be performed based on this study population.

Subjects who do not complete treatment will not be included in the efficacy analyses.

As-Treated Population (AT):

This population consists of all treated subjects regardless of weight change etc.

2.16.3 Endpoint Analysis

Primary Endpoints:

The secondary endpoint of the study will measure subject feeling about body shape, assessed using the Body Satisfaction Questionnaire at the 4-Week follow-up visit. The scale measures body image using a set of ten dichotomous items used to describe aspects of shape and appearance. The items are rated on a five-point semantic differential scale. Mean scores will be tabulated. Differences and percentage change from baseline at the 4-week follow-up visit will be determined.

The primary safety endpoint will be the frequency of device-related adverse events (AEs) including device-related serious adverse events (SAEs). The number and percentage of subjects experiencing each AE will be descriptively summarized. Adverse events and SAEs will be presented as summary tables showing the frequency and type of events.

Secondary Endpoint:

The secondary efficacy endpoint will be the subject rating of improvement of the treatment area based on the SGAIS score 4 weeks after the fourth (final) EMS treatment. Subjects who have reported ‘Very much improved,’ ‘Much Improved,’ and ‘Improved’ will be categorized as ‘Improved.’ The counts and percentage of subjects who noted improvement will be summarized and the 95% confidence interval will be calculated. .

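### The primary BSQ result is planned without a confidence interval, although the secondary SGAIS result has one, and percentage change is a poor summary of a score with no true zero

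*Combined protocol and SAP*

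**What the plan says.** Section 2.15.1 names the primary efficacy endpoint: "Efficacy endpoint: Measurement of subject feeling about body shape, assessed using the Body Satisfaction Questionnaire at the 4-Week follow-up visit". Sections 2.14.2 and 2.14.3 describe one questionnaire for the abdomen and one for the buttocks, each with ten items: "The items are rated on a five-point semantic differential scale". The documents give no item codes, scoring direction or rule for the total.

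The whole planned analysis of this endpoint is in section 2.16.3: "Mean scores will be tabulated. Differences and percentage change from baseline at the 4-week follow-up visit will be determined". For the secondary SGAIS endpoint, the same section gives the number and percentage improved and adds that "the 95% confidence interval will be calculated".

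Section 2.16.1 has a general rule that continuous variables are summarised by mean, SD and range, and states: "The significance level will be two-sided 0.05 for all statistical tests". No test is named for the BSQ. Of the Per-protocol Population, section 2.16.2 says that "the primary efficacy analysis will be performed based on this study population".

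There is also a clerical slip. Under the Primary Endpoints heading, section 2.16.3 opens with "The secondary endpoint of the study will measure subject feeling about body shape". Section 2.15.1 and the Protocol Summary show that the BSQ is primary.

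**The concern.** There are two weaknesses in how the main result would be reported.

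- **Precision.** The plan commits to an interval for the secondary result and not for the primary one. Precision could be modest: 200 is only a maximum (section 2.6), a subject may be treated on the abdomen, the buttocks or both (section 2.12), the BSQ is recorded per body area (Table 2), and the primary analysis is per-protocol. The number behind each area's mean may be well below 200.
- **Percentage change.** A ratio to baseline has a clear meaning only if zero on the scale means none of the quantity. A semantic-differential sum has an arbitrary origin, so the percentage partly reflects where the codes start and which way they run. Section 2.16.3 also does not say whether the percentage is taken on group means or averaged over subjects, and the two can differ.

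At stake is a headline percentage that can make the same raw change look larger or smaller, with no committed statement of how precisely that change was estimated.

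**Working it through.** The plan gives no figure to reproduce: the cap of 200 has no effect size, SD or precision target behind it. From the documents come the ten items, the five points per item, the maximum of 200 and the two-sided 0.05 level. Everything else below is assumed for illustration: item codes, baseline means, SD, correlation, a 5-point change, and 100 or 50 subjects per area.

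**1. Is an interval promised anywhere?** Section 2.16.3 has one for the SGAIS and none for the BSQ. Section 2.16.1 promises SDs for continuous data in general. An interval for paired change needs the SD of the differences; visit-specific SDs are not enough without the correlation. The 0.05 level is attached to no BSQ test. No redaction mark falls within section 2.16.3, so blacked-out text there does not explain the gap.

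**2. Percentage change under different codings.** Take the same improvement of half a point per item, which is 5 points over ten items.

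| Item coding | Baseline to 4 weeks | Percentage change |
|---|---|---|
| 1 to 5 | 25 to 30 | 5/25 = +20.0% |
| 0 to 4 | 15 to 20 | 5/15 = +33.3% |
| 1 to 5, reversed | 35 to 30 | -5/35 = -14.3% |
| -2 to +2 | -5 to 0 | 5/(-5) = -100% |

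The ratio of the first two is 33.3/20.0 = 1.67. As a share of the scale range, the change is 5/40 = 12.5% in size under every coding; for an item mean it is 0.5/4 = 12.5%.

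**3. Group means or per-subject averaging.** With 0 to 4 coding, take baselines of 5, 15 and 25 and a gain of 5 each. The per-subject percentages are 100, 33.3 and 20, with mean 51.1%. The change in group means is 15 to 20, or 33.3%.

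**4. No true change.** Simulation of 2,000,000 bivariate normal pairs per scenario with equal means, rounded and clipped to a 10-50 sum. The table shows the mean per-subject percentage change.

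| SD, r | Higher is better, mean 25 | Lower is better, mean 35 |
|---|---|---|
| 6, 0.5 | +3.44% | +1.63% |
| 6, 0.7 | +2.07% | +0.97% |
| 8, 0.5 | +6.09% | +3.12% |
| 8, 0.7 | +3.70% | +1.88% |

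With higher-is-better scoring this favours treatment. With lower-is-better scoring the same sign is an apparent slight worsening. Percentage change in group means stayed within 0.03 of zero throughout.

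**5. Size of the missing interval.** Change SD = SD × sqrt(2(1 − r)). SD 6 gives 6.00 (r = 0.5) and 4.65 (r = 0.7); SD 8 gives 8.00 and 6.20. Half-width = t(0.975, n − 1) × change SD / sqrt(n), in points:

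| n per area | 4.65 | 6.00 | 6.20 | 8.00 |
|---|---|---|---|---|
| 200 | 0.65 | 0.84 | 0.86 | 1.12 |
| 100 | 0.92 | 1.19 | 1.23 | 1.59 |
| 50 | 1.32 | 1.71 | 1.76 | 2.27 |

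Against an assumed 5-point change, this runs from 0.65/5 = 13% to 2.27/5 = 45%.

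**The case against.** The best defence is that little information would be lost. Differences from baseline are continuous data, so on a natural reading section 2.16.1 gives them an SD, and a reader with n could derive the interval. The study is described as a feasibility evaluation without a comparator, and the visible text sets no success threshold, so no stated decision turns on the interval. The raw difference is reported beside the percentage. One study uses one coding, so the ratio of 1.67 never arises within this trial, and the scoring rule may be on the questionnaire, which is not among the documents. The upward bias needs both per-subject averaging and higher-is-better scoring, and neither is documented.

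Much of this stands, and it limits the weight of the point. The raw change remains interpretable, the simulated bias is conditional, and the numerical sizes rest on assumptions. It does not remove the point. An SD for the paired differences is not expressly promised, and a derivable interval is not a committed one. A confidence interval is itself a descriptive statement of precision, and the plan already gives one for its secondary endpoint. Even with a single coding, the reported percentage depends on an arbitrary origin.

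**Conclusion.** The concern holds. The absence of a planned interval for the primary BSQ endpoint, and its presence for the SGAIS, are plain from the text and need no assumption. That percentage change depends on the coding follows from the type of scale; how far it moves (for example +20% against +33.3%) rests on the assumed codes and baseline. The bias under no change, +2.1% to +6.1% in favour of treatment, applies only with per-subject averaging and higher-is-better scoring, and percentage change in group means avoids it. The half-widths, 0.65 to 2.27 points for 200 down to 50 subjects per area, are illustrative. This is a change that should be made, but it does not threaten the study: the raw differences are planned and the data are collected. The unstated scoring rule and the mislabelled endpoint are missing detail and a clerical slip, and add no weight.

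**What to change.** In section 2.16.3, replace the analysis sentences for the BSQ with wording such as:

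> For each body area (abdomen, buttocks), mean BSQ scores will be tabulated by visit. The mean paired change from Treatment Visit 1 (before treatment) to the 4-week visit in the Per-protocol Population will be reported with its SD and two-sided 95% confidence interval.

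Drop percentage change, or express the change as a percentage of the scale range. In the same edit, add one sentence on scoring (item codes, direction, and sum or mean of the ten items) and correct the label so that the BSQ is called the primary efficacy endpoint.

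The cost is SAP wording only. The BSQ is already completed per body area before the first treatment and at 4 weeks, so no data or visits are added. The percent-improvement figure is lost or replaced. With no control group, the interval shows sampling error only; it cannot separate a treatment effect from expectation or regression to the mean.

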2.17 Protocol Adherence

The study Investigators are responsible for performing the study in compliance with the protocol. Non-adherence to the protocol is to be classified as a protocol violation or protocol deviation as defined below.

Protocol Violation

Non-adherence to the protocol that may result in significant additional risk to the subject (e.g., enrollment of a subject who does not meet the study criteria). Or, non-adherence to Good Clinical Practices (GCP) that may impact patient safety (e.g., failure to obtain proper consent prior to performing study procedures). Violations should be reported to the study Sponsor within 5 working days and reported to the IRB per IRB guidelines.

Protocol Deviation

Non-adherence to study procedures which does not result in additional risk to the subject (e.g., subject missed visit). Protocol deviations are not required to be reported to the IRB; however, they must be recorded on the study case report forms and may be reported and reviewed in conjunction with the progress report as part of the annual review process.

2.18 Adverse Events

Adverse events (AEs) will be assessed continuously throughout the study. An adverse event is defined as any untoward medical occurrence in a participant, regardless of whether the event is related to the device.

All AEs and device deficiencies will be recorded on the corresponding CRF for the subject.

Adverse Device Effect (AE)

Any sign, symptom, or disease in a study participant that occurs during the course of a clinical trial that is determined by the Investigator to have a causal relationship or possible causal relationship with the device under investigation.

Device Deficiencies

A device deficiency is defined in accordance with ISO 14155 as inadequacy of a medical device including issues with respect to its identity, quality, durability, reliability, safety, or performance. Device deficiencies include malfunctions, use errors, and inadequate labeling.

If a device deficiency occurs, the investigational site will document the event using the CRF. Device deficiencies will be documented throughout the study and appropriately managed and reported to regulatory authorities and IRBs as required by Federal regulations.

Serious Adverse Event (SAE)

Any untoward medical occurrence in a participant, regardless of whether the event is related to the device that:

- a. results in death;
- b. results in a life-threatening illness or injury;

The term life threatening in the definition of serious refers to an event in which the participant was at risk of death at the time of the event. It does not refer to an event, which hypothetically might have caused death, if it were more severe.

- c. results in a permanent impairment of a body structure or body function;
 - Impairment of body function means a substantial disruption of a person's ability to conduct normal life functions.
 - This definition is not intended to include experiences of relatively minor medical significance such as uncomplicated headache, nausea, vomiting, diarrhea, influenza, and accidental trauma (e.g., sprained ankle) which may interfere with or prevent everyday life functions but do not constitute a substantial impairment.
- d. requires in-patient hospitalization or prolongation of existing hospitalization;
 - In general, hospitalization signifies that the participant has been detained (usually involving at least an overnight stay) at the hospital or emergency ward for observation and/or treatment that would not have been appropriate in the physician's

office or outpatient setting. Complications that occur during hospitalization are AEs. If a complication prolongs hospitalization or fulfills any other serious criteria, the event is serious. When in doubt as to whether hospitalization occurred or was necessary, the AE should be considered serious. Hospitalization for elective treatment of a pre-existing condition that did not worsen from baseline is not considered an AE.

- e. results in medical or surgical intervention to prevent impairment to body structure or function;
- f. results in fetal distress, fetal death, or a congenital abnormality/birth defect.

Time Period and Frequency for Collecting AE and SAE Information

All AEs and SAEs from the signing of the ICF until the follow-up visit will be collected at the time points specified in the schedule of activities, and as observed or reported spontaneously by study participants.

Medical occurrences that begin after signing of informed consent and before administration of study treatment will be recorded on the Medical History/Current Medical Conditions section of the CRF not the AE section.

Unanticipated Adverse Device Effect (UADE)

Any serious adverse effect on health and safety or any life-threatening problem or death caused by, or associated with a device, if that effect, problem, or death was not previously identified in nature, severity, or degree of incidence in the investigational plan or application, or any other unanticipated serious problem associated with a device that relates to the rights, safety, or welfare of participants.

The Investigator shall be responsible for determination of the causal relationship of all adverse events to the device and/or procedure. The Principal Investigator is responsible for monitoring the safety of the participants enrolled.

Reportable Incidents

Serious adverse events (SAEs) and unanticipated adverse device effects (UADEs) must be recorded and reported to the manufacturer of the study device and to the Sponsor or designee within 24 hours of knowledge of the event.

Sponsor Contact:

ZELTIQ P/N: [REDACTED]
Protocol Number: ZA19-002

[name]
Director, Clinical Trial Management
ZELTIQ Aesthetics, an Allergan affiliate
[name]
[name]

[REDACTED]
[REDACTED]

A full reporting of the event shall be provided within 10 working days of the event. The Sponsor is then responsible for notifying the IRB, as required.

Other adverse events, deemed by the investigator to be non-serious, should be provided to the Sponsor as soon as possible and not later than 1 week after knowledge of the event. This will be forwarded to the Product Surveillance team within 24 hours of receipt by the Sponsor Contact.

Additional information obtained by the Clinical Site regarding any adverse event, both serious and non-serious, will be reported to the Sponsor within 24 hours of awareness.

3. Study Management and Quality Control

3.1 Study Data Collection

Standardized Case Report Forms (CRFs) will be provided to all participating sites. Data will be reviewed by the study monitor and data management to identify inconsistent or missing data and to ensure compliance with the study protocol.

3.2 Confidentiality

All information and data concerning study subjects will be considered confidential, and handled in compliance with all applicable regulations including the requirements of the Health Insurance Portability and Accountability Act (HIPAA) of 1996.

Only authorized site staff, the study Sponsor or the Sponsor's designee, IRB and FDA will have access to these confidential files. All data used in the analysis, reporting and publication of this clinical trial will be maintained without identifiable reference to the subject. Any data that may be published in abstracts, scientific journals, or presented at medical meetings will reference a unique subject code and will not reveal the subject's identity.

3.3 **Investigator Responsibilities**

General Responsibilities

Investigators are responsible for ensuring the investigation is conducted according to all signed agreements, the Investigational Plan, and applicable FDA regulations.

The Investigator must protect the rights, safety, privacy and welfare of the subjects under the Investigator's care. Investigators will assume overall responsibility and accountability for study site staff and for the clinical data obtained during the study.

The Investigator assumes all responsibilities per 21 CFR 812 and other applicable regulations, including but not limited to:

IRB approval: The Investigator may not begin the study until the governing institutional review board (IRB) provide written approval of the study protocol and consent form. The Investigator is also responsible for fulfilling any conditions of approval imposed by the IRB.

Informed Consent: The Investigator must ensure that informed consent is obtained from each prospective study subject in accordance with 21 CFR Part 50 and that the study is not commenced until IRB approvals have been obtained.

Device Accountability: The Investigator is responsible for controlling all investigational device(s) stored at their site, including supervision of device use, disposal of the device or returning the device as instructed by the Sponsor.

Financial Disclosure: Investigators shall provide financial disclosure according to federal regulations (21 CFR 54).

Study Coordinator: To assure proper execution of the study protocol, each Investigator must identify a study coordinator for the site who will work with and under the authority of the Investigator to assure that study requirements are fulfilled as appropriate.

Investigator Records

The Investigator and study staff must maintain accurate, complete, and current records relating to the conduct of the investigation. Records must be retained for a period of two years following (1) the date the investigation was completed or terminated, or (2) the records are no longer required to support a regulatory submission or completion of a product development protocol, whichever is longer. Participating Investigators shall maintain the following:

- All correspondence with the Sponsor, another Investigator, the IRB, or a monitor

ZELTIQ P/N: [REDACTED]
Protocol Number: ZA19-002

- Records of all persons authorized to conduct the study (e.g. Delegation of Duties/Signature Authorization, CV)
- Records of receipt, use or disposition of the devices
- Informed Consent documentation for all enrolled subjects
- Records of each subject's case history, including study-required Case Report Forms and source documentation (e.g. physician notes, lab reports, study worksheets, clinic charts)
- All relevant observations of adverse device effects
- Records of any protocol deviations
- The condition of each subject upon entering and during the course of the investigation and any relevant medical history and results of any diagnostic tests
- Record of each subject's exposure to the devices, including the date and time of use
- Investigational plan with all amendments
- Current IRB approved informed consent and all previously approved versions
- Signed Investigator agreement
- Investigators will be responsible for the accurate and timely completion of CRFs during the trial.

These records must be available and suitable for inspection at any time by Sponsor representatives (monitor) or the reviewing IRB. The Investigator will supply access to study-related medical records, original laboratory data, and other records and data as they relate to the trial. The Investigator will ensure that both he/she and his/her study staff have adequate time and resources to devote to the study, including study enrollment, subject evaluations, study documentation and site monitoring.

Investigator Reports

The Investigator is responsible for preparation and submission of the following reports:

- Report of any unanticipated adverse device effects shall be submitted to the Sponsor within 24 hours and no later than 10 working days after the Investigator first learns of the effect.
- Withdrawal of IRB approval of the Investigator's part in the investigation shall be reported to the Sponsor within 5 working days

ZELTIQ P/N: [REDACTED]
Protocol Number: ZA19-002

- Progress reports on the investigation to the Sponsor, the monitor, and the reviewing IRB annually. Alternatively, the Sponsor may prepare the report.
- Deviations from the investigational plan shall be reported to the Sponsor and the IRB.
- Failure to obtain informed consent prior to use of a device in a subject shall be reported to the Sponsor and IRB within 5 working days after the use occurs.
- A final report shall be submitted to the Sponsor and IRB within 3 months after termination or completion of the investigation, or the Investigator's part of the investigation.

